#### 4. Study Procedures

##### 4.1. Study Design

4.1.1. Describe experimental design of the study. Include sequential and/or parallel phases of the study, including durations, and explain which interventions are standard of care.

*The study design is a 9-month, randomized, 2-arm, parallel, open-label feasibility trial. Eligible participants will be randomized to a brief single Motivational Interviewing (MI) session and SUMMIT versus a pain monitoring app. All participants will also be provided a referral to speak with a clinical pharmacy specialist about their medications and options for tapering. Feasibility and outcomes planned for a full-scale RCT will be collected at one-, three-, six-, and nine-months post-randomization. Opioid dose and adverse events (AEs) will be collected bi-weekly. We will send the link to the questionnaire to the participant if they have given permission to contact via email, otherwise we will send them the link via text, or read it aloud to them. Given the urgency to develop effective programs to support tapering efforts, we will perform interim analyses at three months. If positive, results of these analyses would expedite onset of the planned full-scale RCT.*

*Eligible patients on long term opioid treatment (LTOT) or on buprenorphine will be identified through VA Corporate Data Warehouse (CDW). Receipt of opioid medication will be defined as any dispense of a VA formulary category CN101 drug. Veterans having liquid methadone dispensed in the previous six months will be excluded. Because all methadone for the treatment of OUD is dispensed at federally licensed opioid treatment programs, we will cross check all methadone dispenses with stop code 523, the code used exclusively in those programs. For Veterans who remain eligible, a focused electronic medical record (EMR) review will be conducted to determine whether the Veteran is currently receiving liquid methadone or participating in a concurrent pain or opioid-related research study, and to check for evidence of hearing or visual impairments (not corrected with hearing aids or glasses), cognitive impairment or psychiatric condition. A list of eligible Veterans will be compiled into an Excel file and saved on the secured CHERP server. This list of potential subjects will NOT be printed out.*

*The study team will reach out via email to the primary care providers of Veterans who remain eligible after the above screening, to ensure the provider agrees with approaching the Veteran for possible enrollment.*

*Approved Veterans will then be mailed a letter informing them of the purpose of the study. The letter will notify potential participants that they will be telephoned by the project coordinator and will offer them the opportunity to refuse this contact by calling an answering machine and leaving a message. The project coordinator will telephone all patients who do not "opt out." If someone other than the participant answers the telephone, no personal health information (PHI) will be shared with the person who answers. Five attempts will be made to make contact with the potential participants. Veterans may also be informed of the opportunity to participate in the study by their primary care provider and be provided with a study letter. The study team will contact the Veteran within a week of provision of study letter. Participants will be assured that their participation is voluntary and that they can opt out from participating. During the telephone call, the remaining eligibility criteria will be verified.*

*Up to 64 patients will be recruited to participate in this research study. Due to COVID19, participants will undergo the informed consent process over the telephone, and provide oral consent.*

*All participants will be offered a referral to a clinical pharmacy specialist in the pain clinic to discuss options for medication management and opioid tapering. As part of the informed consent, patients will be reassured that the tapering steps will be conducted by their own pain care provider or with the assistance of the clinical pharmacy specialist.. After obtaining consent, participants will be trained on how to complete baseline and outcome measures on their preferred device. **Surveys will be sent to the participant via email through RedCap. As an alternative, we will register participants into the VA HealtheDialog text messages system in order to receive surveys and access the SUMMIT web application via link.** Baseline measures will be completed during this visit, prior to randomization, to ensure that participants are comfortable completing surveys electronically.*

*Participants will be randomly assigned to the intervention or control group in a 1:1 ratio in eight blocks of eight using the Research Electronic Data Capture (REDCap) Randomization Module.*

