## SECTION 5: HUMAN PARTICIPANT INFORMATION

**NOTE:** A participant is considered "enrolled" at the time the consent is signed so this number should include an allowance for screen failures prior to randomization.

1. **How many participant records will be reviewed PRIOR to enrollment/consent occurring?**  
Approximately 1,280 participants records will be reviewed.

2. **How many participants will be screened PRIOR to enrollment/consent occurring?**  
Approximately 640 participants will be screened assuming 1 enrolled per 10 screened.

3. **How many participants will be enrolled (total number to include randomized and screen failures AFTER consent is obtained)?**

Up to 64 participants will be enrolled.

3.1. Will all research activity be the same at all sites? Yes  No  N/A

3.2. If no, please describe the activity that is different or limited (For example; 2 sites will analyze data only, or, 1 site will consent and enroll all participants etc.): Philadelphia site will consent and enroll all participants and both Philadelphia and West Haven sites will analyze data.

4. Are there any further screening procedures after enrollment? Yes  No

4.1. If yes, describe:

5. **Are non-Veterans being enrolled?** **NOTE:** This does not include non-Veterans enrolled at non-VA sites. Yes  No

5.1. If yes, provide justification.

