3.2. **Provide a brief description of each individual's role in the study. Be sure to indicate who will have access to protected health information and who will be involved in recruiting subjects; obtaining informed consent; administering survey/interview**

procedures; and performing data analysis.

-The PI will have access to all study data, be involved with recruitment, obtaining informed consent and HIPAA authorization, and administering interviews.

-The Co-Investigator and the collaborators will meet monthly with the PI to discuss study design and oversee study progress. The co-investigators and collaborators will be involved with data analysis and will not have access to PHI.

-The research assistant, to be hired, will be involved with recruitment, obtaining informed consent and HIPAA authorization, and administering the initial study visit.

3.3. If applicable provide information on any services that will be performed by contractors including what is being contracted out and with whom.

N/A

3.4. If applicable provide information on any Memoranda of Understandings (MOUs) or Data Use Agreements (DUAs) that are being entered into including with whom and for what reason.

N/A

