## 6. Informed Consent Procedures

6.1. **Indicate if informed consent will be obtained and/or if you are requesting a waiver of informed consent or waiver of documentation of informed consent. If the research involves multiple phases, specify for which phases of the research the waiver(s) is being requested and/or the informed consent will be sought.**  
Informed consent will be obtained. We will be obtaining an oral informed consent in part due to limitations as a result of COVID19. This is due to risks of obtaining in person consent for both patients and study staff. The patient will be contacted via telephone or VA Video Connect for the consent process, and the informed consent form will be read aloud to the participant to ensure full understanding of the purpose of the study, study procedures, as well as the risks and benefits of participating. Once the study coordinator confirms through questioning that the participant fully understands all aspects, oral consent will be documented. A copy will be mailed to the patient and be placed in the patient's chart.

6.2. **Describe who will be obtaining informed consent, if applicable, and any circumstances that may need to be addressed (e.g. subjects with impaired decision making ability and the use of a legally authorized representative, etc.)**  
Study staff, such as the PI or the project coordinator will obtain informed consent.

6.3. **If applicable, indicate how local site study personnel will be trained regarding human subjects' protections requirements and how to obtain and document informed consent.**  
All study staff will be trained/overseen by PI. All study staff will have completed relevant training regarding human subjects protection and how to obtain informed consent. All personnel are required to have CITI (Good Clinical Practices and Ethical Principles), VA Privacy and Information Security Awareness and Rules of Behavior, and Privacy and HIPAA Trainings. In addition, all study staff obtaining informed consent will have taken the VA Research Compliance Officer training.

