## 9. Data Analysis

9.1. Provide sample size determination and analysis (include anticipated rate of screen failures, study discontinuations, lost to follow-up etc.).

The calculated number of participants to be enrolled in this feasibility study was based on the approach outlined by Cocks and Torgerson (85), which recommends using a 1-sided confidence interval (CI) to determine whether it is worthwhile proceeding with a full-scale trial. If the proportion of participants achieving the primary outcome is 20% or lower in the control group (14), the sample size required to detect a difference of 15% in the main trial (assuming 80% power, alpha = 0.05, two-sided test) is 276. (14, 85) A pilot sample size of 48 would produce a one-sided 90% CI that would exclude finding a 15% difference in the larger fully-powered trial. To account for the reasonably high drop-out rate, we will inflate the sample size by 25%. Thus, we will randomize 64 participants.

9.2. Describe how, where and by whom the data will be analyzed.

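### A fixed block size of eight, printed in the protocol of an open-label trial with one enrolling site, makes allocations more predictable than they need to be; a different allocation table would reduce this cheaply

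*Combined protocol and SAP*

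**What the plan says.** All references are to the combined protocol and SAP.

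- **Allocation (Section 16, 4.1.1).** Participants are assigned "in a 1:1 ratio in eight blocks of eight using the Research Electronic Data Capture (REDCap) Randomization Module". This is one fixed block size, and no stratification is mentioned.
- **Masking (Section 16, 4.1.1).** "The study design is a 9-month, randomized, 2-arm, parallel, open-label feasibility trial".
- **Enrolling sites (Section 5, item 3.2).** "Philadelphia site will consent and enroll all participants". West Haven contributes data analysis only.
- **Size (Section 16, 9.1).** "Thus, we will randomize 64 participants".
- **Recruitment and eligibility (Section 16, 4.1.1).** "The project coordinator will telephone all patients who do not" opt out. On that contact, "During the telephone call, the remaining eligibility criteria will be verified".
- **Consent (Section 16, 6.2).** "Study staff, such as the PI or the project coordinator will obtain informed consent".
- **Research assistant (Section 16, 3.2).** This person "will be involved with recruitment, obtaining informed consent and HIPAA authorization, and administering the initial study visit". The same section has the PI recruiting, obtaining consent and holding access to all study data.
- **Who sees the arm (Section 16, 4.1.1).** A study coordinator sets up participants' apps, which differ by arm, in a video appointment. The same section has a study coordinator deliver the motivational interview to the intervention arm only, whereas item 7 of Section 16, 1.2 gives that session to a co-investigator.

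The text does not mention varied block sizes, withholding the block size from recruiters, or separating recruiters from people who learn allocations.

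**The concern.** A permuted block protects the next allocation only as long as its position and composition cannot be worked out. With an unstratified sequence at one site, a known constant block size and visible past allocations, the rest of each block can be deduced by counting. Concealing the future list in the REDCap module does not stop this, because the deduction uses only what has already been revealed.

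Someone with that knowledge could, deliberately or not, influence who enters next or when. The room for this lies before randomization: when to call, when to schedule, and how to judge the final eligibility check. Section 5 expects about 640 people to be screened for up to 64 enrolled. Baseline measures are completed before randomization, so baseline scores are not themselves recorded with the arm known.

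What is at stake is the comparison between arms. Section 16, 9.2 plans regression of the primary and secondary outcomes on group to look for preliminary trends, and a three-month interim look that includes opioid dose reduction. Section 16, 4.1.1 says positive interim results would bring the full-scale trial forward. The sample size in 9.1 rests on a confidence-interval approach to deciding whether to proceed.

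**Working it through.** **The plan's own figure.** Section 16, 9.1 starts from 48 and allows for 25% dropout: 48 / 0.75 = 64. Eight blocks of eight give 8 × 8 = 64. The two agree. The documents give no predictability figure, so the rest is derived here.

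**Inputs.** Block size 2m = 8, so m = 4; 1:1 allocation; one sequence; 64 participants. The person predicting knows the block size and has a complete tally.

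**Certain allocations.** An allocation is certain once one arm has used its m places in the block. The expected number per block is 2m/(m+1) = 8/5 = 1.6, which is 1.6/8 = 20%, or 8 × 1.6 = 12.8 of 64. Enumerating all C(8,4) = 70 possible blocks gives the same mean. The number certain in a block is 1, 2, 3 or 4 with probability 57.1%, 28.6%, 11.4% and 2.9%.

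**Correct guesses.** The strategy is to guess the arm that is behind in the block and toss a coin on ties. The expected number correct per block is m + (2^(2m)/C(2m,m) − 1)/2 = 4 + (256/70 − 1)/2 = 5.329. That is 5.329/8 = 66.6%, or 42.6 of 64. This includes the certain allocations.

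**Alternatives.**

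| Scheme | Certain, of 64 | Guessed correctly |
|---|---|---|
| Eight fixed blocks of 8 | 12.8 | 66.6% |
| Undisclosed random order of 8, 12 and 16, totalling 64 | nearly none; about 1.7, at the end of the list, if staff know the 32:32 total | 64–65% (simulation) |
| Single permuted 32:32 list | 64/33 = 1.9 | 57.1% |

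For the single list m = 32 and 2^64/C(64,32) = 10.07, so the guess rate is (32 + (10.07 − 1)/2)/64 = 57.1%. Varying the block size therefore removes certainty but leaves most of the guessing; the single list reduces both.

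**Illustrative bias (assumption, not from the documents).** Suppose mean prognosis moves by +s under one guess and −s under the other, at every enrolment. With guess rate g, each arm's mean moves by (2g − 1)s in opposite directions, so the arm difference moves by 2(2g − 1)s.

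- Fixed blocks of 8: 2 × (2 × 0.666 − 1) × s = 0.664s. For s = 0.1 to 0.2 SD this is 0.07 to 0.13 SD. The gap between patients entered under opposite guesses is then 0.2 to 0.4 SD.
- If 0.1 to 0.2 SD is the whole gap, s is 0.05 to 0.1 and the bias is 0.03 to 0.07 SD.
- Single list: 2 × (2 × 0.571 − 1) × s = 0.284s, or 0.03 to 0.06 SD for s = 0.1 to 0.2.

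**Sampling error for scale.** The standard error of a standardised arm difference is √(1/32 + 1/32) = 0.25 SD with 64 participants and √(1/24 + 1/24) = 0.29 SD with 48.

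**The case against.** The best case for leaving the plan alone has four parts.

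1. **The harm is small and hypothetical.** The 20% and 66.6% describe a perfect tally-keeper; they are not evidence that anyone will count. Even the upper illustrative bias, 0.13 SD, is about half a standard error (0.13/0.25). Section 16, 9.2 calls most analyses descriptive and says the trial is not powered for between-group differences. This stands, and it sets the priority.

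2. **The room for selection is limited.** Hearing, visual, cognitive and psychiatric exclusions are looked for in the record review. Provider agreement, a mailed letter and the chance to opt out follow, before five telephone attempts. This largely stands. However, Section 16, 5.2 has the inclusion and exclusion criteria confirmed on the call, so some judgement remains at the point of entry, along with call timing and scheduling.

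3. **The overlap of roles is not documented.** A reader might infer that one small team screens, consents, randomises and sees every past allocation. The documents do not say who operates the REDCap module or who builds the table, nor whether the project coordinator and the study coordinator are the same person. The study-team pages are not in the public copy. Overlap is likely, given one site and the roles described, but it is an inference.

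4. **Varying the blocks changes little.** Mixed blocks of 8, 12 and 16 still leave 64–65% guessable. This stands, and it is why the single list is preferred below.

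A reader might also infer that the recruitment rate would be biased. The documents do not support this. Reordering candidates does not change how many of those approached enrol; only delay or refusal would, and nothing shows either.

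**Conclusion.** The point holds as a predictability weakness with a cheap remedy. For staff who know the block size and tally past allocations, 12.8 of 64 allocations (20%) are expected to be certain and 66.6% guessable, and concealing the list in REDCap does not prevent it. These figures are exact for a single unstratified sequence of fixed blocks of eight; they would change if there were strata that the document does not mention.

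That recruiters learn past allocations is likely but inferred. The possible consequence is confined to the exploratory comparison between arms. The bias range of 0.03 to 0.13 SD is an illustration resting on an assumed shift at every enrolment, and should not be read as an expected bias. Confidence is high in the arithmetic and lower in any actual harm. This is a modest improvement, not a flaw that undermines the feasibility aims.

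**What to change.** In Section 16, 4.1.1, replace the eight blocks of eight with one of these:

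- **Preferred:** a single permuted list of 32:32.
- **Alternative:** undisclosed, randomly ordered blocks of 8, 12 and 16 totalling 64. This removes nearly all certain allocations but little of the guessing.

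With either, have the table generated by someone who does not recruit, such as the West Haven analysts, and keep the details of the scheme out of documents that recruiting staff hold. The protocol should also state who runs the randomization module and whether that person recruits. If feasible, keep recruiting staff from seeing the running tally of allocations.

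**Cost.** A new allocation table and a few changed sentences, ideally before the first allocation. The statistical price is a larger possible imbalance mid-trial, at the interim look or if recruitment stops early, most of all with the single list. Fixed blocks of eight never let the arms differ by more than 4 and are balanced after 32 participants. With a single list, the arm difference after 32 has standard deviation 2 × √(32 × 0.25 × 32/63) = 4.0, so a split such as 18:14 would be unremarkable. The final split is 32:32 either way if all 64 are randomized.

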#### ***Randomization groups:***

*Experimental Intervention: Participants randomized to the experimental intervention will participate in a Motivational Interviewing (MI) session lasting between 30 and 60 minutes with a study coordinator. All MI sessions will be audiotaped using a VA-approved digital recorder and transcribed verbatim. Participants will subsequently be shown how to access SUMMIT through a web link via a set of unique anonymized login credentials and to navigate the components of SUMMIT on one or more devices, depending on their preference. They will then be trained on how to complete the outcome surveys **on RedCap, which will be sent via email**.*

*The SUMMIT application includes multiple modules for participants to learn about opioid tapering as well as other ways to manage their pain. As part of the application, participants will also have the option to connect with a peer support specialist at the VA who has previous experience with chronic pain and opioid tapering.*

**Control Intervention:** Participants randomized to the control intervention will use an eHealth comparator: Manage My Pain(iPhone, Android). This app includes a pain monitoring functioning only, and thus will only minimally overlap, if at all, with SUMMIT's components. Control participants will not participate in a MI session. Participants will download the app and be shown how to use the Manage My Pain app and trained how to complete the outcome surveys

In order to help participants set up their mobile applications, the study coordinator will set up a video appointment through the VA's virtual care manager (VCM) and using the VA video connect (VVC) software. The appointment is coordinated using the participants email address, and through the video appointment the coordinator will help the participant set up their device.

**4.1.2. Include a description of how anticipated risk will be minimized and include an analysis of risk vs. potential benefit.**

*Veterans with anxiety or concerns will be referred to their primary care physician. Each Veteran will be assigned an ID number that is not related to any PHI. The key containing the link between the study ID number and participant will be maintained on the CMCVAMC's secure server*

*(\\vhaphifpccherp.v04.med.va.gov\shares2\[name]) on a separate folder from the collected data. Only [name] (PI) and study staff will have access to this key.*

*Neither the SUMMIT app nor the Manage My Pain app will be collecting any personal health information. The SUMMIT app will collect aggregated data on usage of features of the app. The Manage My Pain app once downloaded requires the user to complete an end user agreement that specifies how any collected data will be used and shared. The app does aggregate non-personal information from all users, including pain records, age, geographic location, and gender, which is stripped of personal information. There is an option to sign up for an online account through the Manage My Pain app, which would collect additional information, however study participants will be advised not to do so.*

**4.1.3. Provide description of the study population (delineate all categories of subjects – patients, providers, family members, employees, etc.). Include anticipated enrollment numbers.**

*This projects involves the recruitment of 64 Veterans. Patient recruitment at the CMCVAMC will target male and female patients enrolled in long term opioid treatment (LTOT).*

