7. Motivating veterans to taper LTOT will be challenging. We acknowledge that motivating veterans on LTOT to taper will be difficult as many may be strongly biased to remain with the status quo. We will address this bias by including motivational interviewing (mi) as part of the intervention. Mi is a patient-centered approach that explores and develops patients' motivation and commitment to change within a collaborative, highly empathic patient-provider relationship. Characteristically, providers blend a combination of fundamental patient-centered counseling skills (e.g., reflective listening) with advanced strategic methods to elicit patient statements that favor change, called "change talk." Trained counselors help the patient develop and appreciate discrepancies between important life goals and current behavior; thus, the motivation, while facilitated by the counselor, comes from the patient. Mi has been demonstrated to significantly increase patients' intrinsic motivation for change and to increase self-efficacy for making behavioral changes across multiple conditions. (44-49) in this study, [name] (co-i) will conduct a single mi session with participants randomized to the intervention arm. The use of single session mi is supported by several studies. (50-53)
8. Innovation: how our vision for SUMMIT differs from currently available pain apps. Robust pain self-management skills are critical to enable patients with chronic pain to optimize qol. In view

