## 8. Study Evaluations

8.1. Describe all evaluations to be conducted (including screening; tests/questionnaires that will be administered; any procedures that subjects will be required to complete) and data collection methods. Include materials as an appendix or separate attachment.

The following questionnaires will be delivered through REDCap by the study coordinator at the outset of the study, and then every 6 weeks over the course of the study: Baseline Assessment, Daily Opioid Dose, Prescribed Opioids Difficulties Scale, PHQ-8, GAD-7, Modified Social Support Survey, Change Questionnaire, BIRS-24, PROMIS-29 Profile v2.0, and WHO 5-Item Well Being Scale. Participants will complete the surveys with the study coordinator, who will enter the responses into REDCap.

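### The plan contradicts itself on who gives the motivational interview and on how outcomes are collected; one combination of its statements has intervention participants, but not controls, report outcomes to their own counsellor.

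*Combined protocol and SAP*

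**What the plan says.** **Who gives the motivational interview (MI).** Section 16, 4.1.1 (Randomization groups) has intervention participants attend a "Motivational Interviewing (MI) session lasting between 30 and 60 minutes with a study coordinator". Controls have no MI session. Section 16, 1.2 item 7 says instead that the co-investigator "will conduct a single mi session with participants randomized to the intervention arm". Section 16, 3.2 describes the co-investigator and collaborators as meeting monthly with the PI on design and progress, and adds: "The co-investigators and collaborators will be involved with data analysis and will not have access to PHI". That role list assigns MI to nobody and has no entry for a study coordinator.

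**How outcomes are collected.** Three descriptions stand side by side.
- Self-completion: 4.1.1 says "Surveys will be sent to the participant via email through RedCap", with a text-message link as the alternative. Its paragraph on the experimental arm trains participants to complete outcome surveys "on RedCap, which will be sent via email". Section 14 likewise has assessments completed electronically.
- Link with a fallback: the opening paragraph of 4.1.1 sends a link by email if permitted, "otherwise we will send them the link via text, or read it aloud to them". It does not say who reads.
- Staff-administered: 8.1 lists the battery, including Daily Opioid Dose and the Change Questionnaire, and says "Participants will complete the surveys with the study coordinator, who will enter the responses into REDCap".

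**Who analyses.** Section 16, 9.2 gives the quantitative analysis to the PI and a co-investigator.

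No section describes a blinded assessor or analyst, or separates MI delivery from outcome collection.

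**The concern.** MI is meant to draw out a patient's own commitment to change. Someone who has just voiced that commitment to a counsellor, and is later asked by the same person what dose they take and how ready they are to change, has a reason to answer favourably. In this trial only the intervention arm could be in that position. A coordinator who takes answers in both arms is a counsellor to one arm and a stranger to that conversation in the other.

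Such a pull would act on one arm only and could not be separated from an effect of MI plus SUMMIT. It would matter in two places. Section 16, 9.2 looks at opioid dose reduction at three months as possible support for starting the full-scale trial early. Section 16, 9.1 sizes the pilot on whether its one-sided 90% interval excludes a 15-point difference. Over-reporting of success in the intervention arm would push both towards proceeding.

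The conflict over the provider has its own cost. A feasibility trial should show who can deliver MI in practice, and as written it is unclear whether the result would describe delivery by a coordinator or by a co-investigator.

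**Working it through.** The plan gives no figure on this point, so the check sets the statements side by side and asks what each combination implies.

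**Step 1. Can the two MI statements both hold?** Section 16, 1.2 item 7 names a co-investigator; 4.1.1 names a study coordinator. Each describes the single session given to the intervention arm, so they conflict unless one person holds both titles, which nothing in the text suggests. The first also sits badly with 3.2, because an individual, audio-recorded session is hard to conduct without access to PHI.

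**Step 2. Can the survey statements all hold?** Self-completion through an emailed or texted link and completion with a coordinator who enters the responses are different modes. No section says which governs which survey. The schedules differ too: 8.1 describes a six-weekly battery, while 4.1.1 has assessments at one, three, six and nine months and opioid dose and adverse events every two weeks. It is therefore not settled that 8.1 covers every dose report.

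**Step 3. Cross the two contradictions.**

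| MI given by | Surveys | Is the MI provider also the outcome collector? |
|---|---|---|
| Coordinator (4.1.1) | Self-completed by link (4.1.1, Section 14) | No |
| Coordinator (4.1.1) | Taken with the coordinator (8.1) | Yes, for intervention participants only, if it is the same person |
| Co-investigator (1.2) | Self-completed by link | No |
| Co-investigator (1.2) | Taken with the coordinator (8.1) | No |

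Where a survey is read aloud, the answer depends on who reads, which is not stated.

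**Step 4. Is it the same coordinator?** 4.1.1 refers to a study coordinator and 8.1 to the study coordinator. A project coordinator also appears, for recruitment calls (4.1.1, 5.2) and consent (6.2), but 6.1 gives part of the consent process to the study coordinator, so the two titles may be one post. No second study coordinator is described. One person is the likely reading, but it cannot be proved from the text.

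**Step 5. Does any safeguard break the link?** None is stated. Open-label status in 4.1.1 explains why participants know their arm. It does not require the person who gave the MI to take the answers.

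**The case against.** The strongest reply is that 4.1.1, read on its own, has no problem: the paragraph that gives MI to a coordinator goes on to send outcome surveys by email. Section 14 and the rest of 4.1.1 agree, and the assessor overlap rests on one sentence in 8.1. This stands, and it limits the point. A reader might infer that the MI provider ends up recording or analysing outcomes whichever statements are followed. The table above shows otherwise: with a coordinator giving MI and every survey self-completed, the provider does neither on the text as written.

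A reader might also infer that a co-investigator who gives MI then analyses that participant's data. Section 11, item 5 lists one co-investigator with data access, which makes this plausible. But names are removed, other sections use the plural, and pleasing a counsellor is not a mechanism that works through a REDCap analysis. Section 16, 9.2 also describes most analyses as descriptive and the comparisons as unpowered. This overlap is secondary.

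A third tempting step is to attach a size. With 24 completers per arm (half of the 48 in 9.1), one answer is 1/24 = 4.2 points and four are 4/24 = 16.7 points, above the 15-point target. That holds for any four misclassified answers from any cause. The documents do not support four, or any other number, and the available text does not define the primary outcome, so it is not established that it rests on self-report.

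Finally, a separate collector would not remove all reporting bias in an open-label trial. That is true, but it is no reason to keep a part that can be avoided.

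**Conclusion.** The plan contains two contradictions, one on the MI provider and one on the mode of outcome collection. Together they leave open a combination (MI as in 4.1.1, surveys as in 8.1) in which intervention participants report opioid dose, and motivation through what appears to be the Change Questionnaire, to the person who counselled them on tapering, while controls report to someone who did not counsel them.

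This rests on three conditions: that the 8.1 sentence governs, that one coordinator fills both tasks, and that the outcome concerned is reported by the participant. The first is one of several readings, the second is likely but not provable, and the third is true of the instruments listed in 8.1 but not confirmed for the undefined primary outcome.

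If the bias arises, its direction would favour the intervention. Its size cannot be derived from the documents. It should be resolved before enrolment because the three-month dose trend may be used to bring forward the full-scale trial and the correction is cheap.

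**What to change.** 1. Name one MI provider role and make Section 16, 1.2 item 7, 3.2 and 4.1.1 agree. The choice is the investigators'; 3.2 should then list that role and its access to PHI.
2. Amend 8.1 so that outcome surveys, including Daily Opioid Dose, are self-completed through the REDCap email or text link in both arms, as 4.1.1 already provides. Align the survey schedule between 8.1 and 4.1.1 at the same time.
3. Add to 4.1.1 and 8.1 that help with a survey, or reading it aloud, is given in both arms alike by a listed team member who did not deliver MI to that participant. Section 16, 3.2 lists the PI and a research assistant still to be hired. The PI is also an analyst, and the protocol should say whether the research assistant and the coordinator are the same post.

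The cost is protocol wording and task assignment; if those roles are separate people, no extra staff are needed. The downsides are slightly less scheduling flexibility at a single site and possibly somewhat more missing surveys if fewer are completed with staff. The missing-data summaries already planned in 9.2 would show the latter.
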